5.4 Secondary Endpoint(s) Analysis

5.4.1 Key/Confirmatory secondary endpoint(s)

- Treatment: Zilucoplan administered by daily subcutaneous (SC) injection (0.3 mg/kg) vs matching placebo
- Target Population: is defined through the inclusion/exclusion criteria at Sections 8.1 and 8.2 of the study protocol, reflecting the targeted IMNM population
- Endpoints:
 - At least minimal response based on the American College of Rheumatology/European League Against Rheumatism (ACR/EULAR) Response Criteria Scale at Week 8;
 - Change from Baseline to Week 8 in Triple Timed Up and Go (3TUG) Test (in ambulatory patients only);

- Change from Baseline to Week 8 in Proximal Manual Muscle Testing (MMT);
- Change from Baseline to Week 8 in Physician Global Activity Visual Analogue Scale (VAS);
- Change from Baseline to Week 8 in Patient Global Activity Visual Analogue Scale (VAS);
- Change from Baseline to Week 8 in Health Assessment Questionnaire (HAQ);
- Change from Baseline to Week 8 in MDAAT Extramuscular Disease Activity VAS Score;
- Change from Baseline to Week 8 in FACIT-Fatigue Scale;
- Intercurrent event (ICE) handling: regardless of any treatment discontinuation for any reason; censoring after administration of prohibited medication
- Population level summary:
 - Odds Ratio (OR) and ACR/EULAR ≥ 20 response proportion between treatment conditions;
 - Difference in continuous endpoint means between treatment conditions

5.4.2 Definition of endpoint(s)

- ACR/EULAR response is defined based on the total improvement score, see Section [6.1.5.7](#) for the response criteria. The endpoint of minimal response is defined as achievement of ACR/EULAR ≥ 20 at Week 8.
- Absolute change from baseline to Week 8 of:
 - 3TUG,
 - Proximal MMT,
 - Physician Global Activity VAS,
 - Patient Global Activity VAS,
 - HAQ,
 - Extramuscular Disease Activity VAS Score of MDAAT Score and
 - FACIT-Fatigue Scale.

Change from baseline to Week 8 (CHG_{Week8}) of each secondary continuous endpoint is defined as: $CHG_{Week8} = (Value_{Week8} - Value_{BSL})$.

5.4.3 Main analytical approach

Analysis to determine the OR and the 95%CI of ACR/EULAR ≥ 20 (minimal treatment response) between IMPs will be performed via binary logistic regression with IMP and strata as fixed factors. Bar charts by treatment will be created to illustrate the treatment effect.

In order to assess secondary efficacy for any continuous parameter, a separate linear mixed effect model will be employed for each secondary continuous efficacy parameter. At each linear mixed effect model, the response variable will be the change from baseline to Week 8. Treatment and strata will be fitted as fixed factors whereas baseline levels of the parameter as covariate; participants will be fitted at random. The Kenward-Roger approximation will be used to estimate the denominator's degrees of freedom. The least squares means (LSMs) of each IMP and the least squares mean differences (LSMDs) between the Zilucoplan and placebo will be reported for the Week 8 change from baseline along with the corresponding 2-sided 95% CIs and p-values.

Statistical estimators based on Least Square Means (LSMs) and Standard Errors (SE) or 95% CIs will be plotted for each treatment.

5.4.4 Sensitivity analysis

No sensitivity analysis to be performed.

5.4.5 Supplementary analyses

Analysis mentioned at Section 5.4.3 will be repeated in ITT with missing values imputed based on the LOCF approach from the previous non missing visit of Week 8. Based on this approach, the elements of ACR/EULAR will also be imputed with the last non missing parameter in order the score to be calculated at Week 8.

Analysis mentioned at Section 5.4.3 will be repeated in the ITT_{NOCOVID-19}. In case of non-convergence, only the summary statistics will be reported.

Analysis mentioned at Section 5.4.3 will be repeated in the PPS.

Estimand:

- Treatment: Zilucoplan administered by daily subcutaneous (SC) injection (0.3 mg/kg) vs matching placebo
- Target Population: is defined through the inclusion/exclusion criteria at Sections 8.1 and 8.2 of the study protocol reflecting the targeted IMNM population
- Endpoints:
 - ACR/EULAR of at least minimal response at Week 4;
 - ACR/EULAR ordinal treatment response at Week 4 and Week 8;
 - ACR/EULAR Total Improvement Score at Week 4 and Week 8;
 - Change from Baseline to Week 4 in Triple Timed Up and Go (3TUG) Test (in ambulatory patients only);
 - Change from Baseline to Week 4 in Proximal Manual Muscle Testing (MMT);
 - Change from Baseline to Week 4 in Physician Global Activity Visual Analogue Scale (VAS);

- Change from Baseline to Week 4 in Patient Global Activity Visual Analogue Scale (VAS);
- Change from Baseline to Week 4 in Health Assessment Questionnaire (HAQ);
- Change from Baseline to Week 4 in MDAAT Extra muscular Disease Activity VAS Score;
- Change from Baseline to Week 8 in FACIT-Fatigue Scale;
- Intercurrent event: regardless of treatment discontinuation for any reason; censoring after administration of prohibited medication;
 - Population level summary: Odds Ratio (OR) of ACR/EULAR ≥ 20 response proportion between treatment conditions (analysis will be performed as mention Section 5.4.3).
 - Population level summary: ACR/EULAR ordinal treatment response proportion in treatment conditions;
 - Difference in continuous endpoint means between treatment conditions (analysis will be performed as mention Section 5.4.3).

For the determination of ACR/EULAR response categories, see Section 6.1.5.7. Ordinal ACR/EULAR treatment response (no improvement, minimal improvement, moderate improvement, major improvement) at Week4 and Week 8 will be only be summarized by IMP.

5.5 Tertiary/Exploratory Endpoint(s) Analysis

5.5.1 Long Term Efficacy

- Treatment: Zilucoplan administered by daily subcutaneous (SC) injection (0.3 mg/kg)
- Target Population: is defined through the inclusion/exclusion criteria at Sections 8.1 and 8.2 of the study protocol, reflecting the targeted IMNM population
- Endpoints:
 - At least minimal response based on the American College of Rheumatology/European League Against Rheumatism (ACR/EULAR) Response Criteria Scale at each study visit following Week 8;
 - Change from Baseline in Triple Timed Up and Go (3TUG) Test (in ambulatory patients only) at each study visit following Week 8;
 - Change from Baseline in Proximal Manual Muscle Testing (MMT) at each study visit following Week 8;
 - Change from Baseline in Physician Global Activity Visual Analogue Scale (VAS) at each study visit following Week 8;
 - Change from Baseline in Patient Global Activity Visual Analogue Scale (VAS) at each study visit following Week 8 at each study visit following Week 8;

- Change from Baseline in Health Assessment Questionnaire (HAQ) at each study visit following Week 8;
- Change from Baseline in MDAAT Extramuscular Disease Activity VAS Score at each study visit following Week 8;
- Change from Baseline in FACIT-Fatigue Scale at each study visit following Week 8;
- Intercurrent event (ICE) handling: regardless of any treatment discontinuation for any reason, censoring after administration of prohibited medication
- Population level summary:
 - ACR/EULAR ≥ 20 response proportion;
 - Mean change from Baseline to each extension portion visit

Further summaries by IMP to be provided for each ACR/EULAR response category (no response, minimal response, moderate response and major response) and for the ACR/EULAR TIS.

Analysis will be performed in descriptive manner without any statistical comparisons to be considered.

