7.2.2.2 DISCONTINUATION OF INVESTIGATIONAL MEDICINAL PRODUCT

During the Main Portion, if a subject permanently discontinues study drug at any time prior to completion of Day 57 (see Section 8.4.2), the subject should return to clinic for an End of Main Visit. During the Extension Portion, if a subject permanently discontinues study drug at any time (see Section 8.4.2), the subject should return to clinic for a Final Extension Visit. If a subject discontinues study drug at any time, a 40 day follow up visit is required.

The following procedures will be completed at the End of Main and Final Extension Visits:

- Completion of the following efficacy assessments:
 - 3TUG (in ambulatory subjects only)
 - Proximal MMT
 - Physician Global VAS
 - Patient Global VAS
 - HAQ
 - MDAAT
 - FACIT-Fatigue
- Measurement of weight
- Review and documentation of concomitant medications
- Physical examination
- Vital signs (HR, body temperature, blood pressure in the sitting position)
- 12-lead ECG
- Collection of blood samples for laboratory testing: hematology, chemistry, and coagulation (if applicable)
- Collection of urine sample for urinalysis
- Urine pregnancy testing for females of childbearing potential only
- Record AEs
- Collection of blood samples for the following assessments:
 - ADA sampling
 - PK analysis
 - PD analyses
 - Autoantibody testing
 - Biomarker analysis
- Return of all used and unused study drug syringes to site

All subjects who discontinue study treatment will have a Safety Follow-up Visit 40 days after the last dose of study drug, to collect the following information:

- Review and documentation of concomitant medications
- Physical examination
- Vital signs (HR, body temperature, blood pressure in the sitting position)
- Urine pregnancy testing for females of childbearing potential only
- Record information on ongoing AEs or new SAEs since the last study visit.

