5 STATISTICAL ANALYSES

5.1 General Considerations

- Descriptive statistics for continuous endpoints will include number of participants with available measurements (n), mean, standard deviation (SD), median, 25% and 75% percentiles, minimum and maximum. Confidence Intervals (CIs) will be provided where appropriate. In general, all study endpoints will be summarized descriptively by IMP and overall (if applicable).
- Frequencies and percentages will be presented by IMP for categorical and ordinal variables. Unless otherwise noted, the denominator for percentages will be based on the number of participants included in the respective analysis set.

Participants with missing data can generally be accounted for using the following approaches:

- For summaries of demographics and baseline characteristics: summarize percentages based on all participants in the analysis set and include a “Missing” category (corresponding to participants with missing data for the variable being summarized) as the last row in the list of categories being summarized. Percentages are associated with the missing row so that percentages sum to 100.
- For summaries of efficacy and safety variables, unless otherwise specified: summarize percentages based only on those participants with observed data for the variable being summarized. As the denominator may be different from the number of participants in the

analysis set being considered, the denominator should be displayed in the table. The general format for displaying this will be “n/Nsub (%).”

All percentages will be displayed with one decimal place. No percentage will be displayed for zero counts and no decimals will be presented when the percentage is 100%. If there are no missing data for a variable, then the missing row can be removed for that variable in the shell. If there are no observations in any specific eCRF-specified category, then retain that row and present 0's across the table. E.g., if there are no 'American Indian/Alaskan native' participants in the study but this was one of the Racial Group categories in the eCRF, then retain the row and populate it with 0 values.

Decimal places for descriptive statistics will always apply the following rules:

- “n” will be an integer;
- Mean, SD, and percentiles will use one additional decimal place compared to the original data reported;
- CV [%] will be presented with one decimal place;

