5.1.1 General study level definitions

5.1.1.1 Analysis visit windows

All data will be analyzed based on the visits identified per the schedule of activities in protocol. Mapping to analysis visit windows will not be applied, except for end of treatment (EDV) visits (specified in Section 5.1.1.2.3).

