5.1.1.2.3 Mapping of assessments performed at Early Discontinuation Visit

If a participant prematurely discontinues treatment at any time during the Main Portion, then he/she should return to the clinic for a stand-alone End of Main Visit. Corresponding assessments will be mapped to the next visit scheduled where each assessment is done as per protocol.

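### Long-term efficacy is labelled as regardless of discontinuation, but the Extension data and rules give an observed-case, in effect while-on-treatment, result

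*SAP*

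**What the plan says.** SAP 5.5.1 sets out an estimand for long-term efficacy. Its intercurrent-event strategy is "regardless of any treatment discontinuation for any reason, censoring after administration of prohibited medication". Its summary measures are the ACR/EULAR response proportion at the 20-point threshold and, for the continuous scales, "Mean change from Baseline to each extension portion visit". No inference is planned: "Analysis will be performed in descriptive manner without any statistical comparisons to be considered". The section names no analysis set. SAP 5.1 places efficacy analyses primarily in the ITT population. SAP 4 defines ITT_EXT as those who entered the Extension, but 5.5.1 does not refer to it.

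Four other provisions decide what those summaries will contain.

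- **Denominator.** For efficacy variables SAP 5.1 says to "summarize percentages based only on those participants with observed data for the variable being summarized". It adds that "the denominator should be displayed in the table".
- **Visits.** SAP 5.1.1.1 analyses data by scheduled visit: "Mapping to analysis visit windows will not be applied, except for end of treatment (EDV) visits".
- **Scope of the exception.** SAP 5.1.1.2.3 moves discontinuation-visit assessments to the next scheduled visit, but opens with "If a participant prematurely discontinues treatment at any time during the Main Portion" and refers only to the End of Main Visit.
- **Data after stopping.** Protocol 7.2.2.2 covers the Extension: "During the Extension Portion, if a subject permanently discontinues study drug at any time", the subject returns for a Final Extension Visit with efficacy assessments. The only later contact is the 40-day Safety Follow-up Visit, whose procedure list has no efficacy assessment. SAP 5.1.1.2.2 closes the Extension Period at the Final Extension Visit.

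**The concern.** The declared strategy asks how participants are doing at each Extension visit whether or not they are still taking zilucoplan. That needs efficacy data after stopping, and none are collected. Under the observed-data rule, a participant who stops leaves the denominator of every later visit.

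The Main Portion has a mapping rule for this situation and, in SAP 5.3.4 and 5.4.5, a last-observation-carried-forward analysis for Week 8. The Extension, where follow-up is longest, has neither, and it has no non-responder rule.

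The risk lies in interpretation. The Extension is open-label and its results are descriptive. If those who leave are mostly those doing poorly, the by-visit proportion can rise although nobody has improved. Under the present label, a reader could take that as a durable or growing effect among all who entered.

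**Working it through.** **The plan's own figures.** The documents state no Extension discontinuation rate and no long-term response rate, so there is no figure on this point to reproduce. The one quantitative planning claim, about 95% power for the Week 8 CK comparison, is not affected. It reproduces at 94.8% with the exact Wilcoxon test for 12 versus 12.

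**Step 1: what a stopper contributes.**

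| Time | Efficacy data | Where they go |
|---|---|---|
| Scheduled Extension visits before stopping | Yes | By-visit summaries |
| Final Extension Visit | Yes (own column in SAP Table 1-3) | Not mapped to a scheduled visit |
| 40-day Safety Follow-up | None | Nothing to summarise |
| Later scheduled visits | None | Participant leaves the denominator |

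After stopping, nothing from that participant enters a summary tied to time since Extension entry. The by-visit result is therefore observed-case, in effect while-on-treatment.

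**Step 2: the size of the gap.** Let d be the share of entrants who stopped before a visit, pS the response among those still observed, and pL the response the stoppers would have shown.

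- Reported: pS
- Regardless of discontinuation: (1 - d) x pS + d x pL
- Difference: d x (pS - pL)

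The same expression holds for mean changes, with means in place of proportions. The sign depends only on whether stoppers do worse or better than stayers.

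**Step 3: an integer example.** All counts are assumed except 24, the planned enrolment, taken here as the number of entrants. Six stop, so d = 6/24 = 0.25. Twelve of the 18 still observed respond, so the table shows 12/18 = 66.7%.

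| Stoppers who would respond | All entrants | Reported minus all entrants |
|---|---|---|
| 0 of 6 | 12/24 = 50.0% | +16.7 points |
| 2 of 6 | 14/24 = 58.3% | +8.3 points |
| 4 of 6 | 16/24 = 66.7% | 0 |
| 6 of 6 | 18/24 = 75.0% | -8.3 points |

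SAP 5.1.1.4 shows Extension efficacy by treatment sequence, so each column starts from at most about 12. At the same shares (3 of 12 stop, 6 of 9 respond) the gap is the same: 6/9 = 66.7% against 6/12 = 50.0% up to 9/12 = 75.0%.

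**Step 4: a range.** Take an assumed pS = 70%, with 2, 4, 6, 8 or 10 of 24 stopping.

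| pL | Gap in points, d x (70 - pL) |
|---|---|
| 0% | +5.8, +11.7, +17.5, +23.3, +29.2 |
| 25% | +3.75, +7.5, +11.25, +15.0, +18.75 |
| 70% | 0 throughout |
| 85% | -1.25, -2.5, -3.75, -5.0, -6.25 |

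**The case against.** Three things can fairly be said for the plan as written.

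**Overstatement is not demonstrated.** A reader might infer that the reported response is inflated by the factor 1/(1 - d), for example 1/0.875 = 1.14 when 3 of 24 stop. The documents do not support that. The factor assigns zero response to every stopper. That makes it the distance to a composite estimand, not the error against the strategy 5.5.1 declares; the two coincide only if pL = 0. Lack of efficacy is not a named withdrawal reason in Protocol 8.4.2, although subject or physician decision could cover it. Protocol 7.2 also gives reasons for ending that need have nothing to do with response: the France 18-month limit, approval and local availability, and the sponsor ending development. This objection stands, so the conclusion has to be conditional.

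**The Final Extension Visit is not discarded.** A reader might infer that its data are lost. They need not be: it has its own efficacy column in SAP Table 1-3, and 5.5.1 covers every study visit after Week 8. That also stands. However, Protocol 9.2.3 treats this visit as the last of the Extension treatment period. A separate column could therefore pool early stoppers with completers at very different times since entry, and it does not change the by-visit proportions.

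**Attrition is visible and the stakes are small.** Denominators are displayed, Protocol 12.2.2 promises an Extension disposition, and SAP 5.2 tabulates discontinuations due to adverse events. The objective is exploratory, and 5.5.1 also reports continuous scales, response categories and the total improvement score. All true, and it limits the importance. Still, a shrinking denominator shows neither why people left nor how they were doing, and it does not correct the label.

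**Conclusion.** The mismatch holds on the text alone and needs no assumed rate. The intercurrent-event statement in SAP 5.5.1 is contradicted by the data collection in Protocol 7.2.2.2, the observed-data rule in SAP 5.1 and the Main-Portion-only scope of SAP 5.1.1.2.3. What will be produced is an observed-case, in effect while-on-treatment, summary.

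That summary may overstate long-term response, provided those who stop respond less well than those who stay. Size and direction cannot be determined from the documents. The example's span of +16.7 to -8.3 points rests on assumed counts and shows only how wide the uncertainty is in a group this small.

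The consequence is confined to an exploratory, descriptive objective. The Week 8 primary and secondary analyses are unaffected. The correction is worth making because it is cheap and changes what the Extension tables can be read to show.

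**What to change.** 1. **Relabel.** In SAP 5.5.1, describe the by-visit proportions and means as while-on-treatment/observed-case, and name ITT_EXT as the analysis set.
2. **Add one supplementary row** beside the observed-case ACR/EULAR proportion, labelled as a composite strategy.
   - Denominator: all ITT_EXT participants who could have reached the visit.
   - Non-administrative stoppers count as non-responders at visits after stopping.
   - Excluded: those not yet at the visit, and those ended administratively (data cut-off, France 18-month end, sponsor termination, another supply route).
   - Participants who took prohibited medication stay censored, as 5.5.1 states, unless the row explicitly declares otherwise.
3. **Extend the mapping in SAP 5.1.1.2.3** to the Final Extension Visit, for early stoppers only and not completers. Move each assessment to the next scheduled efficacy visit, in the observed-case summary only. In the supplementary row non-response takes precedence, so the same person is not counted in two ways.

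In the example above, with no exclusions or censoring, the table would show 12/18 = 66.7% observed-case before any mapped values, with 12/24 = 50.0% beneath it.

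**Cost.** SAP wording and one row per response table, with no new visits or data. The supplementary figure will be less favourable, and each reason for stopping must be classed as administrative or not. After Day E117 efficacy visits are every 3 months, so forward mapping can shift a value by up to about that long; a table footnote should say so. Keeping the present label instead would require efficacy visits after stopping drug, which is a protocol change.

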5.5.2 Mechanistic biomarkers

Blood samples for mechanistic biomarker testing [e.g., complement fixation, complement function, complement pathway proteins, autoantibody characterization (titer and immunoglobulin class) and inflammatory markers] will be obtained prior to administration of study drug (within 1 hour of dosing) as indicated at [Table 1–2](#) and [Table 1–3](#).

The analysis of biomarkers pertaining to the pathophysiology of IMNM [e.g., complement fixation, complement function, complement pathway proteins, autoantibody characterization (titer and immunoglobulin class), and inflammatory markers] may provide further insight into the clinical efficacy and safety of Zilucoplan in IMNM participants. Complement protein levels and complement activity will be tested to evaluate response to Zilucoplan and to understand participant characteristics related to variations in response to drug. Markers of inflammation may be tested to assess correlation with complement function and clinical response to Zilucoplan. A list of analytes will be created through review of the literature, ongoing clinical studies, and ongoing exploratory work and may be finalized after completion of the study. The completion of these investigations may be conditional based on the results of this or other clinical studies, and samples may be selected for analysis on the basis of clinical outcome.

The results of the biomarker analysis will be reported separately from the main clinical study report analyses and therefore analysis will not be stated in this document.

5.5.3 Pharmacogenomic analyses (optional)

Participation in the pharmacogenomic assessment is optional, and participants must provide additional consent for the pharmacogenomic analysis. For cases who choose to participate in pharmacogenomic studies, a blood sample is obtained. All genomic analyses will be performed

at an accredited laboratory. Genomic studies (e.g., deoxyribonucleic acid (DNA) sequencing) including exploration of whether specific genomic features correlate with response or resistance to study drug, may be performed. The completion of these investigations may be conditional based on the results of this or other clinical studies, and samples may be selected for analysis on the basis of clinical outcome.

The results of the genomic investigations will be reported separately from the main clinical study report analyses and therefore analysis will not be stated in this document.

